3.3.b. Overview and rationale of study design: We propose a one-year, repeated measures, within-subject design to examine the impact of improved caregiver depression on child asthma outcomes. A CLPM for longitudinal data will be fit using a maximum likelihood structural equation model (SEM) in order to explore longitudinal mediation between asthma outcomes (asthma control, spirometry, QOL) and depressive symptoms. CLPM will test whether caregiver improvement preceded child asthma improvement, and SEM will test whether improved adherence and/or decreased child anxiety/depression mediated the effect. We considered a randomized control trial, but it would not be ethically acceptable to withhold medication from caregivers diagnosed with MDD for the proposed one-year duration of the study. It is unlikely that potential

participants in the study would find this acceptable. Furthermore a controlled design is not necessary since we are not testing the efficacy of antidepressants for depression, but rather the impact of improvement on caregiver depression on the child.

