
Greenphire ClinCard, which can be used as a credit or debit card. Caregivers who are consented and come to our clinic for a baseline assessment but not meet all of the entry criteria will be given \$20 for their time and inconvenience. This smaller payment reflects the generally shorter time required when a participant does not qualify for the study because the assessments stop at the point that an exclusion criterion is identified.

[figure not shown]
3.3.c.i. Inclusion/Exclusion Criteria

Inclusion Criteria: Primary Caregivers (defined as the adult who is primarily responsible for the child’s asthma management): Male or female, ages 18 to 70, primary asthma caregiver of the child, currently meeting criteria for MDD (based on DSM-4 depression symptoms for at least 2 weeks and causing clinically significant distress or impairment in social, occupational, or other important areas of functioning) based on a SCID interview.

Child: Male or female, ages 7-17 years who have a diagnosis of **persistent asthma** as classified by either of the following criteria: **A.** requirement for treatment with daily controller medication; or **B.** symptoms of persistent asthma in children not on a daily controller medication: 1. Daytime symptoms two or more days per week; 2. Rescue bronchodilator use two or more times per week; 3. Nocturnal symptoms two or more nights per month; or 4. Two or more oral steroid bursts in the last year.⁵⁶

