3.3.c.iii. Medication: Caregivers with current MDD will be offered antidepressant treatment from a research psychiatrist at no cost for 52 weeks. All medications used will be FDA-approved for MDD. The antidepressants and augmenting agents selected are widely used. We will provide these to the participants at each visit. This method of dispensing medications is different than in clinical practice where a patient would receive the medication at a pharmacy. We propose to use this method to enhance medication adherence and optimize internal validity of the study. Adherence to medication will be assessed by pill counts. We will use a simplified version of the TMAP MDD algorithm that has been adapted for this study. The algorithm is flexible because participants will potentially enter the study with different treatment histories. The doses of antidepressant will be titrated upward, to the FDA-approved maximum if needed, with the goal of achieving depression remission or full response. If the participant is already taking an antidepressant, they will remain on the prescribed medication until the first evaluation stage required by the algorithm and the doctor will assess how well the medication is working at that stage. If this is the first depressive episode and during the course of the study the participant's depression symptoms improve to the point at which they may no longer require medication, the doctor can evaluate if subject should be tapered off the medication. This would only be after at least 6 months of full remission of symptoms. At any time, the subject is free to decide to discontinue taking medication but can remain in the study under the study doctor's care. This decision will be fully discussed with the study doctor for safety reasons. After 12 weeks a change of medication or augmentation can be performed depending upon level of response. This process is repeated at weeks 24 and 36 at which time additional augmentation strategies are allowed. The

objective is to provide active treatment with careful monitoring of depressive symptoms using remission as the goal. For additional medication and algorithm information see Appendix 2. Due to the known side effect profiles of these medications, ECGs and blood tests will be performed in the study as deemed necessary by clinician judgment.

Table 2. Assessment Schedule (Baseline + 13 assessments)

Instrument	Respondent	Wk 0	Wk 4 – 48	Wk 52	Time
2-SRSD	Caregiver	X			3 min
SCID	Caregiver	X			45-60 min

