
both English and Spanish. This scale has 3-point response options and assesses children's anxiety level within the last 3 months.⁵⁸ The Children's Depression Inventory Full Length (CDI Full Length) is a 27-item self-report scale designed to assess depression in children and validated in both English and Spanish.

The COVID-19 Interview is intended to take into account the impact of the COVID19 pandemic on the factors under study in our research. One goal is to assess whether caregiver depression and child asthma control worsened after the onset of the COVID19 pandemic. We will accomplish this by comparing the severity of caregiver depression and the degree of control of the child's asthma in the months before the COVID19 to the caregiver severity depression of and control of child's asthma during the COVID19. This is data that is collected under the currently approved study protocol. In addition, one of our IRB approved research staff and/or a study psychiatrist will ask the caregivers to report on the perceived impact of COVID19 on their own emotional state and functioning, and on the emotional state and asthma control in their child.

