3.4. Statistical Analyses

Aim 1. Determine if improvement in depressive symptoms in caregivers of children with asthma predicts subsequent improvement in the child's asthma control. A CLPM for longitudinal data will be fit using a maximum likelihood SEM in order to explore reciprocal causation between asthma outcomes and depressive symptoms with lagged effect. A separate model will be constructed for each asthma outcome (e.g. CASI, ACT, steroid bursts). The full CLPM with all cross-lagged paths will test if both the asthma outcomes and depressive symptoms predict each other at subsequent visits. For each full model, paths will connect the value of the depressive symptom score (e.g. HRSD) at each visit to the asthma outcome (e.g. CASI) at each subsequent visit (e.g. 4 weeks later, 8 weeks later). Another set of paths will connect the asthma outcome at each visit to the HRSD at each subsequent visit. The full model will be compared to reduced models containing either the first set of paths or the second set. We hypothesize that the model with the first set of paths will provide a better fit than the second set. The models will be compared on goodness of fit criteria, a non-significant X^2 p-value .05 or more, fit indices .90 or more, RMSEA .05 or less, and significant path coefficients.⁶⁸⁻⁷⁵ Extensive overviews of the use of this CLPM for longitudinal data analyses are given by Cole and Maxwell and MacKinnon.^{70, 75} We will follow Cole and Maxwell's⁷⁰ guidelines for testing the proposed causal relationship, caregivers' depressive symptoms preceding child's asthma outcomes, with longitudinal data using SEM software *Mplus*. We will control for variables that might impact depressive symptoms or asthma response including age, gender and race/ethnicity. The primary analysis for this aim will use CASI scores for the child and caregiver HRSD scores. The HRSD is a widely used clinician-rated depression scale while the CASI scores take into account both asthma symptoms and asthma medication use to treat symptoms. Similar analysis will be conducted using the QIDS-SR as the depression measure and STAI as a caregiver anxiety measure. ACT scores and steroid bursts will be used as well as CASI scores in the analysis.

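### In families followed across COVID-19 onset, the before/during comparison is confounded with time since enrolment, and no model in section 3.4 has a pandemic term

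*Combined protocol and SAP*

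**What the plan says.** Section 3.3.d.ii describes the COVID-19 Interview as "intended to take into account the impact of the COVID19 pandemic on the factors under study". One stated goal is to "assess whether caregiver depression and child asthma control worsened after the onset of the COVID19 pandemic". The method is "comparing the severity of caregiver depression and the degree of control" of the child's asthma in the months before the pandemic with the same measures during it. On the source, the section says "This is data that is collected under the currently approved study protocol", so these are the routine visit scores. It gives no onset date, model, comparison group or term for time since enrolment. It does not say whether each family is compared with itself or all visits are pooled. Caregivers are also asked directly about perceived pandemic impact.

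Three features of the design bear on this. Section 3.3.b states "We propose a one-year, repeated measures, within-subject design", and there is no control arm. Section 3.3.c.i requires caregivers to be "currently meeting criteria for MDD". Section 3.3.c.iii has antidepressants titrated "with the goal of achieving depression remission or full response".

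In section 3.4, Aim 1 controls for variables "including age, gender and race/ethnicity". Aim 2 uses site, baseline depressive and asthma symptoms and season, with optional further baseline variables. Aims 3 and 4 follow the Aim 1 approach. None of them mentions the interview or the pandemic period.

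**The concern.** A caregiver selected for current depression and then offered treatment is expected to score lower as follow-up goes on, through regression to the mean and treatment response. For a family whose follow-up spans onset, every before-visit is an earlier study week than every during-visit. The difference between the two therefore contains the ordinary time course as well as any pandemic effect, and the two push in opposite directions if the pandemic made things worse. The plan's question is whether matters worsened, so the risk is a missed worsening or an apparent improvement.

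The second issue concerns the main models. Section 3.3.d.ii itself anticipates effects on both the caregiver's emotional state and the child's asthma, which makes the pandemic a plausible common cause of the two series linked in Aim 1. The panels are indexed by study visit and entry is staggered, so onset falls at different visits in different families and visit-specific intercepts cannot absorb it. Season of the year, in Aim 2, does not represent a one-time event.

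**Working it through.** The plan gives no effect size, sample size or power for this comparison, so there is no figure of its own to reproduce. The check sets the pandemic effect to zero and asks what the comparison would return.

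**Inputs from the plan.** Pilot HRSD 20.9 at baseline and 15.5 at exit after 6 months, n = 8, p = 0.08 (section 3.3.a.ii, Table 1). Baseline plus 13 visits at 4-week intervals to week 52 (section 3.3.c, Table 2). Enrolment over 4 years, or 208 weeks (section 3.3.c.ii).

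**Assumed.** The shape of the HRSD path, constant entry, and the timing of onset.

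**Within family, fall stops at week 24.** The fall per visit is 5.4 / 6 = 0.9. The path is 20.9, 20.0, 19.1, 18.2, 17.3, 16.4, 15.5, then 15.5 for seven more visits. The quantity is the mean of during-visits minus the mean of before-visits.
- Onset after the first visit: before = 20.9; during = (91.0 + 8 × 15.5) / 13 = 16.54; difference = -4.36.
- Onset midway, after seven visits: before = 18.2; during = 15.5; difference = -2.7.
- Onset before the last visit: before = (111.9 + 7 × 15.5) / 13 = 16.95; during = 15.5; difference = -1.45.
- Average over all 13 possible onset gaps: -2.83.

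**Within family, other shapes.** If the 5.4 points are spread evenly over 52 weeks, the step is 5.4 / 13 = 0.415. The two means are always 7 visits apart, so the difference is 7 × 0.415 = -2.9 for every onset. An exponential fall with an 8-week constant gives -1.10 to -5.01, average -2.34. The sign is negative throughout.

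**Pooled over all families, fall stops at week 24.**

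| Onset, weeks after enrolment opens | Mean study week before / during | All visits | 6 months either side |
|---|---|---|---|
| 26 | 7.4 / 26.6 | -2.46 | -1.88 |
| 52 | 16.0 / 27.4 | -1.15 | -0.50 |
| 104 | 22.7 / 28.0 | -0.54 | 0.00 |
| 156 | 24.0 / 29.3 | -0.54 | 0.00 |
| 208 | 24.6 / 36.0 | -1.15 | -0.88 |
| 234 | 25.4 / 44.6 | -1.40 | -0.47 |

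The bias follows the imbalance in mean study week. It vanishes for the short window when entry is steady on both sides of onset.

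**Simulation of the within-family case.** Further assumptions: between-person SD 4.5, residual SD 4, individual response multiplier with mean 1 and SD 0.9, and onset equally likely in any visit gap. With no pandemic effect, a paired t test at 0.05 declares significant improvement in 76–90% of runs with 20 spanning families and in 97–100% with 40. It never declares significant worsening.

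**Effect of adjustment, 40 spanning families.** Adjusted means with person and visit-week terms; the two values are for the path flat after week 24 and the exponential path.
- True effect 0: unadjusted -2.8 and -2.4; adjusted -0.04 and -0.04.
- True worsening +2: unadjusted -0.8 and -0.3, the wrong sign; adjusted +2.1 and +2.0, with SD about 0.7.

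**The case against.** The plan does not say that the comparison is within family, and it neither specifies nor rules out a model: the sentence sits in an instrument description. A reader might infer that a raw comparison is planned and must show depression improving. The documents do not support that. With entry staggered over 4 years, a pooled comparison has early and late study weeks on both sides of onset, and the table shows that the bias can be small or nil. This part of the objection stands and limits the claim about direction to families followed across onset. It does not remove the point, because the comparison as written carries no safeguard and the favourable window is not specified.

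The size is also open to challenge. It comes from eight caregivers with p = 0.08. Treatment is offered, not required (section 3.3.c), and no uptake figure is given. Section 3.5 expects many caregivers to remain symptomatic, and Aim 2 allows for some who worsen. A reader might extend the pilot slope to week 52 and obtain 7 × 0.9 = 6.3 points of bias. That path would put mean HRSD at 20.9 - 13 × 0.9 = 9.2, and nothing in the documents supports it.

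A reader might also infer that asthma control would be answered in the wrong direction. Pilot asthma symptoms did fall (PASS 19.4 to 13.3), but children can qualify on controller use alone, so poor control at entry is not required. Season adds a further imbalance of unknown sign. The same mechanism may operate there, but its size is not shown.

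Finally, this is one goal of an added interview and not one of the four aims. The perceived-impact questions do not depend on the contrast, and the wording of the Aim 1 covariate list leaves it open to additions. These facts lower the weight of the point. They do not supply the missing terms.

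**Conclusion.** The concern holds in limited form. For families followed across onset, the stated comparison is confounded with study week. With no pandemic effect it would return about -1.5 to -4.4 HRSD points if the pilot fall stops at week 24, or about -2.9 if the same fall is spread over 52 weeks. A true worsening smaller than that would be hidden or reversed. Under all-visit pooling with steady entry, the bias is about -0.5 with mid-enrolment onset and up to about -2.5 with onset near the start. It is near zero for a short symmetric window during steady entry.

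The direction for spanning families rests on the entry criterion and treatment intent. The size rests on an eight-person pilot and an assumed path. The documents give neither the timing of onset within enrolment nor the number of spanning families. The effect on asthma control is plausible but unquantified.

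The absence of a pandemic term from section 3.4 is a plain omission, given the interview's stated purpose. Its effect on the Aim 1 to 4 estimates has not been calculated here.

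**What to change.** Pre-specify the onset date. Replace the before/during comparison with a visit-level mixed model for HRSD, and the same for CASI and for ACT, with a person effect, study week, calendar season, site and a pandemic-period indicator. Staggered entry is what allows this: families at the same study week, some before and some after onset, separate the pandemic period from the time course.

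As sensitivity analyses, carry the pandemic into the four aims:
- **Aims 1, 3 and 4:** add the visit-level indicator to both series in each panel model, with its effects constrained equal across visits.
- **Aim 2:** add the share of each family's follow-up that falls in the pandemic period. A visit-level indicator cannot enter this model, which uses one 52-week count and one HRSD slope per family.

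The cost is no new data and a modest amount of extra analysis. Each panel model gains at least two parameters. Without the equality constraint it would gain about 2 × 13 = 26, on top of the roughly 200 paths in the Power paragraph, which is why the constraint is needed. Aim 2 gains one. Adjusting for study week also costs some precision in the pandemic estimate.

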
The baseline assessment will take approximately 2.5 hours and will consist of a 45-60 minute structured clinical interview (SCID) using DSM-4 criteria to establish psychiatric diagnoses, depression, quality of life, and other assessments (see Table 2 for a complete list), as well as information about number of asthma-related hospitalizations, ER visits, and unscheduled clinic appointments by the child within the preceding 12 months as assessed by caregiver report (and confirmed through medical records when possible). Caregivers not meeting criteria for the intervention study will be paid for the initial assessment, informed of any psychiatric disorders identified (e.g. a psychiatric disorder other than MDD) and, when appropriate, given referral information. Caregivers with current MDD and meeting all inclusion criteria will be offered algorithm-based depression pharmacotherapy for 52 weeks. If a caregiver does not elect to participate in the algorithm-based treatment, they will remain eligible to enroll in the study and will receive referral information for an alternative depression treatment (e.g., psychotherapy) from a study psychiatrist. The caregiver will be still eligible to enroll in pharmacotherapy during a later stage of the study and will be advised by a study psychiatrist if they elect this option. Furthermore, participants who are currently receiving or plan to receive treatment for depression (e.g. medication, psychotherapy) by a healthcare provider outside of the study may also participate. In these cases the participants will receive all of the assessments and physician evaluation but will not receive algorithm-based treatment as part of the study. This protocol modification should improve enrollment by allow potential participants who prefer psychotherapy or want to receive antidepressant care from their PCPs to enroll. Given the inclusion, exclusion and discontinuation criteria, as well as the careful monitoring during the study this change should not adversely impact the safety profile of the study. The change is scientifically sound because the aims of the study are related to relationships between depressive symptom changes in the caregiver and asthma control in the child regardless of the method by which the changes were achieved. A total of 196 caregivers will be enrolled. A modified and simplified version the Texas Medication Algorithm Project (TMAP) MDD guidelines (Appendix 2) will be utilized to guide treatment. Caregivers and children will be assessed every four weeks (weeks 4, 8, 12, 16, 20, 24, 28, 32, 36, 40, 44, 48 and 52) with additional phone assessments 2 weeks after medication changes to assess for adverse events, medication side effects, or suicidality, and to confirm the next clinical appointment. Follow-up assessments will take approximately 1.5 hours including psychiatrist assessment and quality of life, asthma adherence, anxiety and depression questionnaires administered by a research team member. Caregivers will be assessed by a study psychiatrist at appointments for medication management. Caregivers will be paid \$60 for the baseline visit and assessments every 4 weeks (weeks 4-52). Children will be paid \$20 at each visit. Bus, rail, or taxi expenses will be reimbursed if these transportation methods are needed. Both caregivers and children will be paid using a UT Southwestern issued

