Buffalo: The Buffalo pediatric asthma service ([name], co-I) that will be used for enrollment is a three-site practice with a diverse patient demographic. The main clinic site is an inner-city clinic attached to the Women and Children's Hospital of Buffalo. In addition, there is a suburban satellite clinic and a suburban/rural satellite clinic. The Buffalo pediatric asthma service has 1160 patients in the age range proposed for the study and 315 new patients in this age range each year. Given these numbers, if 26% of caregivers have current MDD (as in our pilot study), then over a 4 year enrollment period the site will have 547 eligible participants. To enroll 98 participants, 18% of these will need to agree to participate.

Participant retention: We will use established methods for recruiting and retaining populations over long periods of time. Drs. [name] and [name] have used these methods throughout their multi-visit studies and obtained excellent retention statistics (95% completion of a 6 week study). [name] (PI) was an investigator on TMAP, a large multisite study using treatment algorithms for one year in patients with psychiatric illnesses in a similar fashion as the proposed study. In the MDD module of TMAP, retention was 100% at 3 months, 99.5% at 6 months, 83.2% at 9 months and 75.9% at 12 months. To maximize retention in the proposed study, multiple contact numbers (home, cell, work, family, friends), mailing addresses, and e-mail addresses will be obtained. Participants will be compensated appropriately for participation, transportation, time, and effort. Participants will have contact with research staff every 2-4 weeks either by phone or in person to keep them engaged in treatment. Participants are in the study for 52 weeks even if they miss some appointments, and we will collect as much data from each participant as possible. It is noteworthy that our data analytic procedures have robust methods of dealing with missing data. In addition, we propose enrolling 196 participants, rather than the 175 needed based on a power analysis, to allow for some early attrition.

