3.3.d.iv. Asthma Severity, Control and Outcomes: Asthma outcome measures to be used in this study will adhere to the recommended asthma clinical research core outcome measures recently proposed by the NIH's Asthma Outcomes Workshop.⁶⁰ We will incorporate information on asthma exacerbations, healthcare utilization, pulmonary function, quality of life, composite control scores, and asthma symptoms into our outcome measures. Exacerbations will be assessed by caregiver report at each study visit. Exacerbation outcomes will include systemic steroid courses, asthma-specific hospitalizations, asthma-specific emergency department visits/urgent care visits, and asthma-specific intensive care unit admissions/intubations since the last appointment. Healthcare utilization relating to each child's asthma will be assessed, including asthma-specific hospitalizations, asthma-specific emergency department visits/urgent care visits, asthma-specific outpatient visits, and asthma-specific medication use. The number of asthma-specific hospitalizations, emergency department visits and unscheduled clinic appointments by the child in the prior year and during the 1 year of the intervention will be assessed by caregiver report using a calendar to facilitate recall. This information will be supplemented with data obtained directly from the child's hospital, primary physician/asthma specialist, and pharmacy records.

Spirometry data, including % predicted of FEV₁, forced vital capacity (FVC), and FEV₁/FVC ratio will be collected on the child at all study visits using a portable spirometer (EasyOne Plus, NDD Medical Technologies, Inc. Andover, MA).

As a measurement of asthma control, the Asthma Control Test (ACT) will be administered to children ages 12+ at each caregiver depression study visit and the Childhood Asthma Control Test (cACT) will be administered to children ages 5-11.^{61, 62} The ACT and cACT tools represent a continuum of asthma control assessment tools across childhood age ranges. In both tools, a score of > 19 signifies controlled disease and scores of ≤ 19 signifies uncontrolled asthma. Thus, the scores can be combined in the data analysis.

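### Aim 1 steroid-burst counts cover unequal periods after a missed visit, which can mimic a depression-first path if missed visits rise with HRSD

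*Combined protocol and SAP*

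**What the plan says.** - **Collection (3.3.d.iv).** "Exacerbations will be assessed by caregiver report at each study visit". "Exacerbation outcomes will include systemic steroid courses", and the list closes with "asthma-specific emergency department visits/urgent care visits, and asthma-specific intensive care unit admissions/intubations since the last appointment". The text does not say whether the last appointment is the last one attended or the last one scheduled.
- **Visit schedule (3.3.c).** "Caregivers and children will be assessed every four weeks", which gives 13 visits after baseline.
- **Missed visits (3.3.c.ii, participant retention).** "Participants are in the study for 52 weeks even if they miss some appointments".
- **Analysis (3.4, Aim 1).** A separate cross-lagged panel model is fitted for each asthma outcome, with paths from HRSD at each visit to the outcome at every later visit. CASI with HRSD is primary. In addition, "ACT scores and steroid bursts will be used as well as CASI scores in the analysis". No window length, rate or offset is given for steroid bursts.
- **Exposure adjustment (3.4, Aim 2).** Conversion to events per month appears only here, for 52-week totals of ER visits, hospitalizations and unscheduled appointments.
- **Missing data (3.4).** The structural equation models rely on FIML, and missing at random is the working assumption.

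**The concern.** Aim 1 rests on temporal order: caregiver depression changes first and the child's asthma follows. The model lags have this meaning only if each visit's value refers to the same length of time. Under the stated counting rule a missed visit has no value of its own, and its steroid courses are reported at the next attended visit. That value then covers two intervals but enters the model as one.

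If depressed caregivers are more likely to miss a visit, a high HRSD score is followed by a longer counting window and so by a larger recorded count, with no change in the child. The artefact runs in the direction that the study hopes to show.

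**Working it through.** **Plan's own figures.** The documents give no figure for missed visits, burst rate or counting window. The detectable effects in the Power paragraph (f² = 0.10 for 10 predictors and 0.31 for 78 paths, n = 175, 80% power) reproduce as 0.098 and 0.309 with an omnibus F test at an assumed two-sided alpha of 0.05. This point does not touch them.

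**Step 1: size of the window.** With k consecutive missed visits, the next attended value covers 4(k + 1) weeks: 8 weeks after one miss (expected count × 2) and 12 weeks after two (× 3). For a constant miss probability p, the mean window at an attended visit is 4/(1 − p): 4.4 weeks at p = 10%, 5.7 at 30% and 6.7 at 40%.

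**Step 2: why FIML does not repair it.** FIML treats the missed visit's value as unobserved. Here its events have been added to the next observed value, so the observed value itself is wrong for its label.

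**Step 3: false slope on an 8-week path with no true effect.** Let r be the burst rate per 4 weeks and m(h) the probability that the visit in between is missed when HRSD two visits back is h. With both end visits attended, the expected count is r × (1 + m(h)). The slope relative to r, per HRSD SD, is therefore [m(+1 SD) − m(−1 SD)]/2. The miss probabilities below are assumptions.

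| Missed at −1 SD vs +1 SD | Odds ratio per SD | Slope / r per SD |
|---|---|---|
| 10% vs 20% | √2.25 = 1.5 | (0.20 − 0.10)/2 = 5% |
| 10% vs 30% | √3.86 = 2.0 | (0.30 − 0.10)/2 = 10% |
| 10% vs 40% | √6.00 = 2.4 | (0.40 − 0.10)/2 = 15% |

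This takes missing to depend on HRSD at the previous visit. If it depends on HRSD at the missed visit itself, the slope shrinks roughly by the visit-to-visit correlation of HRSD. At an assumed 0.5 it is 2.5% to 7.5%. If missing is unrelated to HRSD, m is flat and the slope is zero.

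**Step 4: how often a null trial would reject.** These are simulations with no true effect, n = 175 and 0.1 to 0.2 bursts per 4 weeks, using lagged regressions rather than the full cross-lagged model. Miss probabilities are those in the table.

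| Test | Rejections |
|---|---|
| All 8-week pairs pooled, missing follows previous visit's HRSD | 9% to 36% |
| All 8-week pairs pooled, missing follows same visit's HRSD | 6% to 17% |
| One unpooled 8-week path | 4% to 8% |
| Pooled, counts divided by weeks covered | 3% to 8% |

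A second grid used 0.05 to 0.20 bursts per 4 weeks, 10% to 30% of visits missed, and missing tied to same-visit HRSD with an odds ratio per 7 HRSD points. Pooled 8-week rejections were 5% to 8% at odds ratio 1.0, 4% to 12% at 1.5, 7% to 19% at 2 and 7% to 25% at 3. The worst cell at 12 weeks was 34%.

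**Step 5: which lags are touched.** In pairs of adjacent attended visits the window is 4 weeks, and no bias appears. Under FIML it does. In a large-sample check with odds ratio 2, the 4-week coefficient was about +0.10 (20% missed) and +0.16 (30% missed) of the base rate per HRSD SD. The summed HRSD effect fell from 0.14 to 0.01 and from 0.21 to 0.00 once counts were divided by weeks covered. Cells with missing unrelated to HRSD gave sums within about ±0.03, which is the noise in this check.

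**The case against.** The strongest reply is that nothing in the documents links missed visits to depression, and without that link there is no false path. This stands, and it makes the conclusion conditional. The retention figures in 3.3.c.ii do not fill the gap: they describe dropout, and only a missed visit followed by a return moves events between windows.

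Second, the larger rejection rates come from pooling all 8-week pairs. Section 3.4 states no equality constraints, and the Power paragraph counts 78 separate paths (13 × 12/2). On a single 8-week path the test stays close to 5%. This also stands: the high figures apply only if paths are constrained equal or pooled.

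Third, the last appointment could mean the last scheduled one. Then events are not carried forward, but those of a missed interval are never collected by report. Either reading needs defining.

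Fourth, 3.3.d.iv mentions a recall calendar and pharmacy records, and 3.3.c.ii plans staff contact every 2 to 4 weeks. These could date the courses. The plan ties the calendar to hospitalizations, emergency visits and unscheduled appointments, and does not say that steroid courses will be reassigned to visit intervals. The mitigation is available but not specified.

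A reader might also infer a fault at week 0, because it has no earlier appointment. The 12-month baseline look-back ends with "unscheduled clinic appointments by the child within the preceding 12 months" and lists no steroid courses. The plan's count of 13 occasions suggests that baseline may not enter the model (14 occasions would give 14 × 13/2 = 91 paths). Week 0 matters only if it is used.

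**Conclusion.** The counting rule and the Aim 1 steroid-burst model do not fit together once visits are missed. Read as events since the last attended visit, one missed visit doubles the next expected count, and neither the model nor FIML corrects it. If missed visits rise with HRSD, this can produce a spurious path in the hypothesised direction. Under the assumed miss probabilities and burst rates the false slope is about 3% to 15% of the base rate per HRSD SD. A pooled 8-week test rejects in about 6% to 36% of null trials, while a single unpooled path rejects in about 4% to 8%. Under FIML the 4-week path can be affected too.

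Three stronger readings are tempting and not supported:

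- That a false path will occur: this needs a link between HRSD and missed visits, for which the documents give no figure.
- That the primary Aim 1 result is compromised: CASI is affected only if its exacerbation domain is scored since the last appointment, and its look-back is not stated.
- That Aim 2 shares the fault: its totals run over the year, so moving events between visits does not change them in this way.

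Confidence is high on the mechanism and low to medium on its size. It is worth correcting because the correction is cheap.

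**What to change.** 1. Record the date of each systemic steroid course. For Aim 1, assign each course to its fixed 4-week study interval, including intervals whose visit was missed.
2. Alternatively, analyse the count per weeks covered, for example with log(weeks since the last attended visit) as an offset. This removes the inflation, but the value still averages over more than one interval, so dating keeps the lag structure cleaner.
3. Define the last appointment as attended or scheduled. If week 0 enters the model, give its steroid-course value a 4-week look-back.
4. State the look-back of the CASI exacerbation domain, and apply the same intervals if it is scored since the last appointment.
5. Report missed visits by prior HRSD, so that readers can judge whether the condition for bias was met.

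The cost is one date field per course and a few sentences in section 3.4. The drawback is recall over 8 weeks or more to date courses in missed intervals, which pharmacy records could support.
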